#### 5.3.2 Key Secondary Endpoints

- Proportion of subjects with Hb values within the target range (10.0 to 11.0 g/dL, inclusive) at the primary evaluation period (Weeks 10 to 12)
- For subjects who transitioned to TIW vadadustat dosing, mean change in Hb from primary evaluation period (average Hb from Weeks 10 to 12) to the secondary evaluation period (average Hb from Weeks 18 to 20)

#### 5.3.2.1 Other Secondary Endpoints

- Mean change in Hb between Baseline (average pretreatment Hb) and the secondary evaluation period (average Hb from Weeks 18 to 20)
- Proportion of subjects with Hb values within the target range (10.0 to 11.0 g/dL, inclusive) at the secondary evaluation period (Weeks 18 to 20)
- For subjects who transitioned to TIW vadadustat dosing, proportion of subjects with Hb values within the target range (10.0 to 11.0 g/dL, inclusive) at the secondary evaluation period (Weeks 18 to 20)
- Proportion of subjects with a mean increase in Hb from Baseline to the primary evaluation period  $\geq 0.5$  g/dL (average Hb from Weeks 10 to 12) or with Hb values within the target range (10.0 to 11.0 g/dL, inclusive) at the primary evaluation period (Weeks 10 to 12)
- Proportion of subjects with a mean increase in Hb from Baseline to the secondary evaluation period  $\geq 0.5$  g/dL (average Hb from Weeks 18 to 20) or with Hb values within the target range (10.0 to 11.0 g/dL, inclusive) at the secondary evaluation period (Weeks 18 to 20)
- Intravenous (IV) iron supplementation

- ESA rescue
- RBC transfusion

### 5.3.2.2 Exploratory Endpoints

## 5.4 PK/PD Endpoints

An exposure-response analysis of vadadustat and PD measures will be conducted as deemed appropriate.

The PK parameters will include (but not limited to) the following:

- Area under concentration-time curve from dosing to last measurable concentration (AUClast)
- Area under concentration-time curve from dosing to infinity (AUCinf)
- Cmax
- Apparent total body clearance (CL/F)
- Apparent volume of distribution (Vd/F)
- Terminal half-life (t1/2)

The PD parameters will include (but are not limited to) the following:

- EPO
- Reticulocytes
- Iron
- Ferritin
- TIBC
- Hepcidin

## 5.5 Safety Endpoints

Safety endpoints in this study include the following:

- AEs
- Vital sign measurements and clinical laboratory values
- Hb >12.0 g/dL, >13.0 g/dL, or >14.0 g/dL
- Hb <8.0 g/dL and decline in Hb  $\geq$ 0.5 g/dL from Baseline Hb (Main Study);  
Hb <7.5 g/dL and decline in Hb  $\geq$ 0.5 g/dL from Baseline Hb (ESA hyporesponder parallel study)
- Hb increase >1.0 g/dL within any 2-week interval

## 6 STUDY DESIGN

[figure not shown]
### 6.1 Study Design

This is a Phase 2, randomized, open-label study to evaluate vadadustat for the treatment of anemia in hemodialysis subjects converting from epoetin alfa therapy.

For all subjects (Main study and ESA hyporesponder parallel study), the study (as shown in [Figure 1](#)) will include a Screening Period, a study Treatment Period, and a Safety Follow-Up Period as described below. PK and PD sampling will be done throughout the study (see PK and PD Sampling [Section 9.2.2.1](#), PK/PD Sampling for Subjects Randomized to Vadadustat and [Section 9.2.2.2](#), PK Sampling for Subjects Randomized to Epoetin Alfa, respectively, for details).

The aim is to achieve and maintain Hb levels within the target range of 10.0 to 11.0 g/dL, inclusive, while targeting the middle of the range and minimizing excursions outside the target range.

## FIGURE 1:OVERVIEW OF STUDY DESIGN

ESA: erythropoiesis-stimulating agent; Hb: hemoglobin; n: number of subjects; SV: screening visit; TIW: three times per week; W: week

### 6.1.1 Screening Period (up to 28 days; Day -28 to Baseline/Day 1)

For all subjects (Main study and ESA hyporesponder parallel study), the Screening Period starts at the time the informed consent is signed and will be a maximum of 28 days in duration. Baseline/Day 1 will be performed within 28 days of the start of Screening. Subjects who meet all eligibility criteria will be randomized to a vadadustat treatment arm or an epoetin alfa treatment arm. Subjects will be required to stop epoetin alfa treatment for a minimum duration of 5 days before Baseline/Day 1 in the Main study and for a minimum of 2 days before Baseline/Day 1 in the ESA hyporesponder parallel study. In the Main study, randomization will

be stratified by the mean weekly epoetin dose calculated over a period of 8 weeks prior to Screening Visit 2 (SV2):

- Low epoetin alfa dose group ( $\leq 90$  U/kg/week) or
- High epoetin alfa dose group ( $> 90$  to  $< 300$  U/kg/week)

### **6.1.2 Study Treatment Period (Baseline/Day 1 to Week 20)**

For all subjects (Main study and ESA hyporesponder parallel study), the Treatment Period will run from Baseline/Day 1 to Week 20. Dose will be adjusted to achieve and maintain Hb levels within the target range of 10.0 to 11.0 g/dL, inclusive, while targeting the middle of the range and minimizing excursions outside of the target range.

#### **6.1.2.1 Vadarustat Treatment**

Subjects in the Main study randomized to vadarustat:

- Subjects in the low epoetin alfa dose group will start vadarustat at an initial, randomly allocated dose of 300 or 450 mg daily.
- Subjects in the high epoetin alfa dose group will start vadarustat at an initial, randomly allocated dose of 300, 450, or 600 mg daily.

Subjects in the ESA hyporesponder parallel study randomized to vadarustat:

- Subjects will receive a starting dose of vadarustat 600 mg daily.

Transition to TIW for all subjects randomized to vadarustat:

All subjects randomized to vadarustat (Main study and ESA hyporesponder parallel study), who complete the 12-week once daily dosing regimen and who meet all the Week 12 transition criteria for switching from daily to TIW dosing, will initiate TIW dosing at a starting dose one tablet greater (+150 mg) than the final dose in the daily dosing period (see [Section 8.4.5.2](#), Transition of Vadarustat Once Daily Dosing to TIW Dosing Regimen).

**Note:** Subjects who are not eligible to switch from daily vadarustat to TIW dosing at Week 12 will remain on daily dosing from the remainder of the study (see [Section 8.4.5](#), Vadarustat Dosing Regimen and Guidelines for Dose Adjustment).

#### **6.1.2.2 Epoetin Alfa Treatment**

Subjects in both the Main study and ESA hyporesponder parallel study randomized to epoetin alfa:

All subjects randomized to epoetin alfa will receive TIW dosing for the entire Treatment Period based on the subject's central laboratory Hb value and the approved epoetin alfa US Package Insert (PI) for adult patients with CKD on dialysis. Dose will be adjusted to achieve and maintain Hb levels within the target range of 10.0 to 11.0 g/dL, inclusive, while targeting the middle of the range and minimizing excursions outside of the target range (see [Section 8.4.4](#), Epoetin Alfa Dosing Regimen).

### 6.1.3 Safety Follow-Up Period (Weeks 20 to 24)

For all subjects (Main study and ESA hyporesponder parallel study), the 4-week Safety Follow-up Period starting at Week 20 will be followed by a post-treatment safety assessment conducted at the beginning of Week 24.

## 6.2 Rationale for Study Design

The Main Study and the ESA hyporesponder parallel study will evaluate different starting doses of vadadustat based on pre-baseline ESA doses. Numerous studies have demonstrated that hemodialysis patients requiring higher ESA doses to treat their anemia have a higher burden of comorbidities, a more inflammatory state, and a greater risk of adverse outcomes (Besarb 1998; Parfrey 2005; Unger 2010). As described above (Section 4.2, Summary of Clinical Experience) in a Phase 2 hemodialysis study (CI-0011), a post-hoc analysis suggested higher pre-baseline ESA doses were associated with lower observed mean Hb levels. Subjects on higher pre-baseline ESA doses may benefit from a higher starting dose of vadadustat after initial conversion from ESAs.

Three levels of pre-baseline ESA dose will be evaluated. In the Main Study subjects will be randomized to one of two cohorts based on pre-baseline ESA dose ( $\leq 90$  U/kg/week and  $>90$  to  $<300$  U/kg/week). The ESA threshold of 90 U/kg/week was based on the median ESA doses reported in the US Renal Data System and US Dialysis Outcomes and Practice Patterns Study, which ranged from approximately 90 to 110 U/kg/week.

The ESA hyporesponder parallel study will evaluate subjects with Hb levels below the target range despite receiving  $\geq 300$  U/kg/week of epoetin alfa. This ESA threshold was based on the definition of resistance to ESAs proposed in the ERA-EDTA 2004 guidelines (Locatelli 2004).

The Main study and the ESA hyporesponder parallel study incorporate an approach to vadadustat dose adjustment designed to maximize the probability that Hb can be maintained within the target range of 10.0 to 11.0 g/dL, inclusive (see Section 8.4.5, Vadadustat Dosing Regimen and Guidelines for Dose Adjustment). The approach to vadadustat dose adjustment in this Phase 2 study includes several modifications as compared to the vadadustat dosing algorithms used in previously completed Phase 2 studies and the dosing algorithm used in the ongoing Phase 3 studies.

During this study, dose increases for vadadustat will be allowed at 4-week intervals, with the exception of the initial 2 weeks of treatment, in the daily and TIW dosing periods of the study. Dose increases will be permitted in the initial 2 weeks of treatment, in the daily and TIW dosing periods, in subjects with a Hb decline  $\geq 0.5$  g/dL from baseline and Week 12, respectively. This approach is commonly used in clinical practice to treat patients with declining or low Hb values (Pfeffer 2009a; Singh 2006). Risk of abrupt or excessive increases in Hb is minimized due to the underlying Hb trajectory and is further mitigated by close Hb monitoring.

In the present study, the safety and efficacy of a vadadustat TIW dosing regimen is being evaluated as a potential alternative treatment regimen to a once daily dosing regimen in hemodialysis subjects. Specifically, this study will evaluate conversion from once daily dosing to TIW dosing. As described above (Section 4.2, Summary of Clinical Experience), the 16-week Phase 2 hemodialysis study evaluated hemodialysis subjects switching from ESA to vadadustat 450 mg TIW for an 8-week fixed-dose period followed by 8 weeks of dose adjustment according to Hb response. The primary efficacy analysis in CI-0011 using observed data showed stable

mean Hb levels in this group. Six of 31 (19%) subjects withdrew due to worsening anemia, and a sensitivity analysis imputing missing Hb values using LOCF demonstrated a decline in mean Hb levels. To maximize the probability that subjects treated with vadadustat TIW will maintain Hb levels within the target range, this study will: examine subjects successfully treated with daily dosing converting to TIW dosing; allow for earlier dose increase after 2 weeks of initial treatment; and permit dose increases up to 900 mg TIW.

### 6.3 Dose Justification

In this study, vadadustat starting daily doses will be determined by pre-baseline ESA dose ([Section 8.4.5](#), Vadadustat Dosing Regimen and Guidelines for Dose Adjustment). In the Main study starting doses of vadadustat will be 300 and 450 mg daily in subjects converting from epoetin alfa doses  $\leq$ 90 U/kg/week and 300, 450, and 600 mg daily in subjects converting from epoetin alfa doses  $>$ 90 to  $<$ 300 U/kg/week. For the ESA hyporesponder parallel study, the starting doses will be 600 mg daily. As described above ([Section 4.2](#), Summary of Clinical Experience), the maximum vadadustat starting dose evaluated in completed Phase 2 NDD-CKD studies was 630 or 600 mg daily, in Study AKB-6548-CI-0005 (CI-0005) and Study AKB-6548-CI-0021 (CI-0021) respectively, and in completed Phase 2 DD-CKD studies was 450 or 600 mg in Study CI-0011 and Study AKB-6548-CI-0022 (CI-0022), respectively.

Based on the dosing algorithm, vadadustat will be titrated to achieve and maintain Hb levels within the target range of 10.0 to 11.0 g/dL, inclusive. The dose range for titration is 150 to 900 mg daily or TIW. Doses of 150 to 630 mg daily have been evaluated in studies evaluating subjects with NDD-CKD and DD-CKD. The maximum vadadustat dose evaluated in healthy volunteers was 1200 mg in a single dose study (CI-0001 and CI-0010) and 900 mg daily in a 10-day multiple dose study (CI-0002), as described in [Section 4.2](#), Summary of Clinical Experience. This study is the first study to examine vadadustat doses of 750 and 900 mg in DD-CKD subjects.

The justification to evaluate higher doses is that to date, dose-ranging clinical studies have not identified a vadadustat dose at which a plateau in exposure or effect has been observed. In Phase 1 studies in healthy volunteers, dose-proportional increases in AUC and  $C_{max}$  and dose-related increases in serum EPO were observed up to the maximum doses studied, single doses of 1200 mg and multiple doses of 900 mg daily for 10 days (CI-0001, CI-0002). In Phase 2 studies in anemic NDD-CKD and DD-CKD subjects, dose-dependent increases in Hb were observed up to the maximum dose studied of 600 or 630 mg daily (CI-0005, CI-0021, CI-0022). It is anticipated that daily doses of vadadustat at 750 or 900 mg, which yield an increase in systemic exposure above 600 mg of approximately 25% and 50%, respectively, would yield an incremental erythropoietic effect greater than 600 mg for the treatment of anemia associated with CKD.

From a safety and tolerability standpoint, as described above ([Section 4.2](#), Summary of Clinical Experience), multiple doses of 700 and 900 mg daily for up to 10 days (CI-0002) and single doses of 1200 mg (CI-0001, CI-0010) have been examined in healthy volunteers. Vadadustat demonstrated dose-proportional PK and achieved serum EPO concentrations up to 34.4 mIU/mL, levels considered physiologic and below exposures achieved with injectable ESAs ([Besarb 1992](#)). A higher incidence of AEs in the gastrointestinal SOC – nausea, diarrhea, abdominal pain, dyspepsia – was observed in groups treated with 700, 900, or 1200 mg compared with lower vadadustat doses or placebo. Most AEs were mild to moderate, short-lived

(1 or 2 days), and assessed as unrelated by investigators. No AEs led to study withdrawal, and no SAEs were reported. No clinically meaningful changes or abnormalities in vital signs, safety laboratory studies, or ECG parameters were reported.

Assessment of animal-to-human safety margins is presented in the Investigator Brochure.

This study design mitigates the risk of vadadustat doses of 750 or 900 mg. Intensive Hb monitoring, a strict dose adjustment algorithm, and phlebotomy will be implemented to mitigate the potential risk of a rapid Hb rise, as follows:

- Hb measurements are scheduled at least every 2 weeks to Week 20
- The dose adjustment algorithm will target a narrow Hb range, 10.0 to 11.0 g/dL, inclusive
- The protocol specifies that phlebotomy may be considered in the setting of high Hb levels (>14.0 g/dL) or a high Hb rate of rise, based on the investigator's judgment

Importantly, the Phase 2 studies demonstrated that cessation of treatment resulted in prompt reduction in mean Hb within 2 to 4 weeks.

## 7 SELECTION AND WITHDRAWAL OF SUBJECTS

### 7.1 General Criteria

To be eligible for this study, a subject or their legally acceptable representative must provide valid informed consent and the subject must meet all eligibility criteria. No study procedures (including Screening tests) may be performed until after the informed consent has been legally signed.

### 7.2 Inclusion Criteria

Subjects must meet the following inclusion criteria:

1.  $\geq 18$  years of age
2. Receiving chronic, outpatient in-center hemodialysis (TIW) for ESRD for at least 12 weeks prior to Screening
3. Maintained on IV epoetin alfa therapy for 8 weeks prior to and including Screening through SV2
4. Eligibility in the Main study and ESA hyporesponder parallel study is based on the following mean weekly epoetin alfa doses:
  - Main study: Mean weekly epoetin alfa dose  $< 300$  U/kg/week for 8 weeks prior to SV2
  - ESA hyporesponder parallel study: Mean weekly epoetin alfa dose  $\geq 300$  U/kg/week for 8 weeks prior to SV2
5. Two Hb values measured by the central laboratory at least 4 days apart between SV1 and SV2 as indicated below:
  - Main study: 2 Hb values between 8.5 and 11.0 g/dL, inclusive
  - ESA hyporesponder parallel study: 2 Hb values between 8.0 and 10.0 g/dL, inclusive
6. Serum ferritin  $\geq 100$  ng/mL and transferrin saturation (TSAT)  $\geq 20\%$  during Screening
7. Folate and vitamin B12 measurements  $\geq$  lower limit of normal during Screening
8. Hemodialysis adequacy as indicated by single-pool Kt/Vurea  $\geq 1.2$  using the most recent historical measurement within 8 weeks prior to or during Screening
9. Understands the procedures and requirements of the study and provides written informed consent and authorization for protected health information disclosure.

### 7.3 Exclusion Criteria

Subjects must not meet any of the following exclusion criteria:

1. Anemia due to a cause other than CKD (e.g., sickle cell disease, myelodysplastic syndromes, bone marrow fibrosis, hematologic malignancy, myeloma, hemolytic anemia, thalassemia, or pure red cell aplasia)
2. Active bleeding or recent blood loss within 8 weeks prior to randomization
3. RBC transfusion within 8 weeks prior to randomization
4. Anticipated to discontinue hemodialysis during the study
5. Judged by the investigator that the subject is likely to need rescue therapy (ESA administration or RBC transfusion) immediately after enrollment in the study

6. History of chronic liver disease (e.g., chronic infectious hepatitis, chronic autoimmune liver disease, cirrhosis or fibrosis of the liver)
7. Aspartate aminotransferase (AST)/serum glutamic oxaloacetic transaminase (SGOT), alanine aminotransferase (ALT)/serum glutamic pyruvic transaminase (SGPT), or total bilirubin >1.5 x upper limit of normal (ULN) during Screening. Subjects with a history of Gilbert's syndrome are not excluded.
8. Current uncontrolled hypertension as determined by the investigator that would contraindicate the use of epoetin alfa
9. Acute coronary syndrome (hospitalization for unstable angina or myocardial infarction), surgical or percutaneous intervention for coronary, cerebrovascular or peripheral artery disease (aortic or lower extremity), surgical or percutaneous valvular replacement or repair, sustained ventricular tachycardia, hospitalization for heart failure (HF) or New York Heart Association Class IV HF, or stroke within 12 weeks prior to or during Screening
10. History of new or recurrent malignancy within 2 years prior to and during Screening or currently receiving treatment or suppressive therapy for cancer. Subjects with treated basal cell carcinoma of skin, curatively resected squamous cell carcinoma of skin, or cervical carcinoma in situ are not excluded.
11. History of deep vein thrombosis or pulmonary embolism within 12 weeks prior to or during Screening
12. History of hemosiderosis or hemochromatosis
13. History of prior organ transplantation (subjects with a history of failed kidney transplant or corneal transplants are not excluded)
14. Scheduled organ transplant from a living donor and subjects on the kidney transplant wait-list who are expected to receive a transplant within 6 months
15. History of a prior hematopoietic stem cell or bone marrow transplant (stem cell therapy for knee arthritis is not excluded)
16. Known hypersensitivity to vadadustat, epoetin alfa, or any of their excipients
17. Any prior use of a HIF-PH inhibitor or any use of an investigational medication within 30 days or 5 half-lives of the investigational medication (whichever is longer), prior to randomization
18. For female subjects:
  - Of non-childbearing potential
    - Inability to confirm surgical sterility (e.g., hysterectomy, bilateral tubal ligation, bilateral oophorectomy) at least 1 month prior to Screening, or
    - Not considered post-menopausal (no menses for >1 year with follicle stimulating hormone [FSH] >40 U/L at Screening)
  - Or, if of childbearing potential,
    - Lack of confirmation of the use of acceptable forms of contraception\* for a minimum of one complete menstrual cycle prior to Screening
    - Positive serum pregnancy test at SV2

- Unwilling to use two acceptable forms of contraception\* (at least one of which must be a barrier method) starting Baseline/Day 1, throughout the Treatment Period and for 30 days after the final study drug administration  
(refer to [Section 9.1.5](#), Contraception and Pregnancy Avoidance Measures)
- 19. Breastfeeding during Screening or throughout the Treatment Period and for 30 days after the final study drug administration.
- 20. Donation of ova starting at Screening, throughout the Treatment Period, and for 30 days after the final study drug administration.
- 21. Male subjects who have not had a vasectomy and do not agree to the following: use of an acceptable form of contraception\* (refer to [Section 9.1.5](#), Contraception and Pregnancy Avoidance Measures) during the study and for 30 days after the last dose of the study drug; to not donate semen during the study and for at least 30 days after the last dose of vadadustat.
- 22. Subjects with bilateral native nephrectomy.
- 23. Any other reason, which in the opinion of the investigator, would make the subject not suitable for participation in the study.

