
	
ii. Not considered post-menopausal (no menses for >1 year with follicle stimulating hormone >40 U/L at Screening)
 
b. Or, if of childbearing potential
 

i. Lack of confirmation of the use of acceptable forms of contraception* for a minimum of one complete menstrual cycle prior to Screening

ii. Positive serum pregnancy test at SV2

iii. Unwilling to use two acceptable forms of contraception* (at least one of which must be a barrier method) starting Baseline/Day 1, throughout the Treatment Period and for 30 days after the final study drug administration

 
19. Breastfeeding during Screening or throughout the Treatment Period and for 30 days after the final study drug administration.
 
20. Donation of ova starting at Screening, throughout the Treatment Period, and for 30 days after the final study drug administration.
 
21. Male subjects who have not had a vasectomy and do not agree to the following: use of an acceptable form of contraception* during the study and for 30 days after the last dose of the study drug; to not donate semen during the study and for at least 30 days after the last dose of vadadustat.
 
22. Subjects with bilateral native nephrectomy.
 
23. Any other reason, which in the opinion of the investigator, would make the subject not suitable for participation in the study.
 
* Acceptable forms of contraception include:
 

• Established use of oral, injected or implanted hormonal methods of contraception.

• Placement of an intrauterine device or intrauterine system.

• Barrier methods of contraception: condom or occlusive cap (diaphragm or cervical/vault caps) with spermicidal foam/gel/film/cream/suppository.

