### **9.1.5 Contraception and Pregnancy Avoidance Measures**

In nonclinical animal embryo-fetal development and fertility studies, there was no evidence of teratogenicity, no skeletal or visceral malformations, and no changes in male or female reproductive and fertility indices, or in sperm parameters. In rats, decreased fetal body weight and reduced skeletal ossification were noted at the highest dose tested of 160 mg/kg/day. Peri-postnatal development studies of vadadustat in the rat are ongoing, and there are no data on the transmission of vadadustat in breast milk or the effect of vadadustat on infants.

Although the potential risk of vadadustat on the developing fetus is limited based on studies to date, the study requires that all subjects must agree to use adequate contraception throughout the study and for 30 days after the last dose of study drug.

Adequate contraception for subjects is defined as follows:

- For females of non-childbearing potential
  - Confirmation of surgical sterility (e.g., hysterectomy, bilateral tubal ligation, bilateral oophorectomy) at least 1 month prior to Screening, or

- Post-menopausal (no menses for >1 year with FSH >40 U/L at Screening)
- For females of childbearing potential
  - Subjects must confirm the use of acceptable forms of contraception\*, for a minimum of one complete menstrual cycle prior to Screening.
  - Must have a negative serum pregnancy test at SV2.
  - Starting Baseline/Day 1, subjects must use two acceptable forms of contraception\* (at least one of which must be a barrier method) throughout the Treatment Period and for 30 days after the final study drug administration
- For males subjects who have not had a vasectomy must agree to the following: use of an acceptable form of contraception\* during the study and for 30 days after the last dose of the study drug; to not donate sperm during the study and for at least 30 days after the last dose of vadadustat.

\* *Acceptable forms of contraception include:*

- *Established use of oral, injected or implanted hormonal methods of contraception.*
- *Placement of an intrauterine device or intrauterine system.*
- *Barrier methods of contraception: condom or occlusive cap (diaphragm or cervical/vault caps) with spermicidal foam/gel/film/cream/suppository.*

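### Exclusion criterion 18 joins two negated conditions with 'or', so it conflicts with Section 9.1.5 on which women of non-childbearing potential may enter

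*Protocol*

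**What the plan says.** Section 7.3 opens its list with the rule "Subjects must not meet any of the following exclusion criteria", so one listed condition is enough to exclude. Criterion 18 then splits female subjects into two branches. The branch for non-childbearing potential has two limbs. The first concerns surgery: "Inability to confirm surgical sterility (e.g., hysterectomy, bilateral tubal ligation, bilateral oophorectomy) at least 1 month prior to Screening, or". The last word of that limb ties it to the second, which concerns menopause and reads "Not considered post-menopausal (no menses for >1 year with follicle stimulating hormone [FSH] >40 U/L at Screening".

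The other branch starts "Or, if of childbearing potential" and carries the contraception and pregnancy-test conditions. The synopsis repeats the two limbs with the same connecting word.

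Section 9.1.5 states the matching rule in positive form. For women of non-childbearing potential, contraception counts as adequate on either of two grounds. The surgical ground is "Confirmation of surgical sterility (e.g., hysterectomy, bilateral tubal ligation, bilateral oophorectomy) at least 1 month prior to Screening, or". The alternative ground, sufficient without the surgical one, is "Post-menopausal (no menses for >1 year with FSH >40 U/L at Screening".

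Sections 9.2.2 and 9.3.1.2 and footnote [n] of Appendix A call for an FSH test at the second screening visit in post-menopausal women, without reference to surgical sterility. Section 13.2 requires the sponsor to be notified of any subject who entered without satisfying the entry criteria, and it does not allow waivers.

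**The concern.** Criterion 18 appears meant as the negative of the rule in Section 9.1.5. The negative of 'sterile or post-menopausal' is 'neither sterile nor post-menopausal'. The criterion instead excludes a woman who lacks either one.

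Eligibility criteria are audited as they are written. A site that applies Section 7.3 to the letter turns away women whom Section 9.1.5 treats as adequately covered. A site that follows Section 9.1.5 enrols women who meet a written exclusion, and under Section 13.2 that is a deviation to be notified. With about 40 sites planned, practice could differ between them. At stake are consistent screening and a clean deviation record.

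**Working it through.** The check is one of logic. The Protocol gives no figure on this point, so there is none to reproduce.

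**Inputs**

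- S: surgical sterility confirmed at least 1 month before Screening (Sections 7.3 and 9.1.5).
- P: post-menopausal by the menses and FSH definition (same sections).
- Criterion 18 as written: exclude if (not S) or (not P).
- Section 9.1.5: adequate if S or P.
- Exact negation of Section 9.1.5: not (S or P) = (not S) and (not P).

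**All four combinations**

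| S | P | Criterion 18 as written | Section 9.1.5 | Limbs joined with 'and' |
|---|---|---|---|---|
| yes | yes | not excluded | adequate | not excluded |
| yes | no | excluded | adequate | not excluded |
| no | yes | excluded | adequate | not excluded |
| no | no | excluded | not adequate on these grounds | excluded |

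As written, criterion 18 matches Section 9.1.5 in 2 of 4 rows (the first and last). The conflict lies in the two middle rows: the sterile woman who is not post-menopausal, and the post-menopausal woman who is not sterile. With 'and', the match is 4 of 4.

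**Does other text repair the two middle rows?**

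- The second branch of criterion 18 is an alternative for women of childbearing potential, so it does not reach these women.
- The synopsis has the same structure; its second limb begins "Not considered post-menopausal (no menses for". Both statements of the criterion therefore carry the fault.
- The reference to Section 9.1.5 inside criterion 18 of Section 7.3 points to the section it conflicts with. It stands after the childbearing items, and the synopsis version lacks it.
- The FSH test at the second screening visit would have little purpose if menopause alone could not qualify a woman. It shows the intended rule but does not change the wording of the exclusion.

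**The case against.** The best reply is that the intended rule is easy to recover. Section 9.1.5 states it plainly, the FSH test fits it, and the literal reading would admit, among women of non-childbearing potential, only those who are both sterile and post-menopausal. Few investigators would screen that way, so the practical effect may be small. That stands, and it is why the point is minor. It does not remove the conflict, because the operative exclusion list still says something else in two places.

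It can also be said that Section 9.1.5 defines adequate contraception and is not an eligibility list. That is true of its heading. But it requires all subjects to agree to adequate contraception, and criterion 18 sends the reader there, so the two have to agree.

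A further objection concerns structure. Both limbs sit under a heading for women of non-childbearing potential. If Section 9.1.5 defines that group, a woman who is neither sterile nor post-menopausal belongs in the other branch, where she can be eligible with contraception. Joining the limbs with 'and' then leaves a branch that should apply to nobody. This is correct and bears on the choice of fix.

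A reader might infer more than the Protocol supports:

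- That the two sections give opposite eligibility. They agree in two of four combinations; 'inconsistent' is the accurate word.
- That a sizeable, countable share of the sample is affected. The Protocol gives neither the expected share of women nor the share who would qualify by one route only, and any count would also need an assumption about how many sites read the criterion literally.
- That the per-protocol population would shrink. Section 11.2 removes subjects only for major deviations affecting the primary endpoint analyses. The primary endpoint is change in Hb, and nothing in the Protocol links a woman's sterility or menopausal category to that analysis.

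**Conclusion.** The point holds as an internal inconsistency. Criterion 18, in Section 7.3 and in the synopsis, read literally excludes two groups of women whom Section 9.1.5 accepts, and no other current text corrects it. The conclusion rests on the wording alone and needs no numerical assumption. The possible consequences are uneven screening and avoidable deviation notifications under Section 13.2. Their extent cannot be computed from the Protocol and depends on how sites read the criterion. No effect on the primary analysis or on the per-protocol population is shown. Severity is low: worth correcting at the next amendment, and no threat to the trial's conclusions.

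**What to change.** Reconcile criterion 18 with Section 9.1.5 in both Section 7.3 and the synopsis, in one of two ways.

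1. Join the two non-childbearing limbs with 'and', so that the exclusion applies only when neither surgical sterility nor post-menopausal status is confirmed. This changes one connecting word in two places.
2. Classify first. State that a woman is of non-childbearing potential if she meets Section 9.1.5 (sterile or post-menopausal), and apply the childbearing-potential conditions only to women who do not meet that definition. This is a short redraft in two places. It also removes the branch that would otherwise apply to nobody.

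The second is the cleaner structure; the first is enough to remove the contradiction. Replacement wording that excludes women for not meeting the definition of non-childbearing potential should be avoided. It would contradict the heading above it and, if read as applying to all female subjects, would shut out every woman of childbearing potential. Neither option needs new data, procedures or changes to the analysis.
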